Basic descriptive statistics for all outcome measures assessed both pre- and post-intervention. Internal consistency estimates, minimum and maximum scores, means and standard deviations are computed for each variable. To test for meaningful change over time, the change in mean score from Time 1 to Time 2 for each outcome measure was evaluated. Formal paired samples t-tests were conducted to test for statistical significance. However, given the small sample size and limited power, we also interpret Cohen's *d* as a more meaningful indicator of the magnitude of the observed effects.

Application Type
General Information
UNCC Personnel
Investigators Outside of UNCC
Conflict of Interest
Exemption
Research Location
Participants
Recruitment
Informed Consent Process
Study Methods and Procedures
Data Management
Benefits, Risks, Safety
Existing Data, Records, Specimens
Incentives and Costs
Study Attachments
PI Certification
Assignment
Review
All Pages

Application Type

Instructions

Before moving to the next page, carefully review the application type definitions listed below and then choose the application type that is appropriate for your research. This will populate the required protocol application pages for you to complete.

Application Type Definitions:

Initial Application: This application is for studies that will involve interaction, engagement, intervention, communication, etc. with human subjects. This may be direct or indirect (e.g., online surveys, use of survey panels, etc.) interactions.

Initial Application - Data Only: The application is for studies that will ONLY ever use data or biospecimens and NEVER have any direct interaction, engagement, intervention, communication, etc. with human subjects.

- Existing data refers to data you will receive or obtain from a source other than your study participant.
- Data obtained from secondary sources and not from the data collection procedures being proposed as part of this study.
- For example, if your study will involve existing data for secondary data analysis (e.g., student records, medical records, administrative data, etc.).
- Note, if you are conducting collaborative research and will be conducting data analysis for the larger collaboration, the IRB Reliance Agreement application type may be appropriate.

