Background and Context information: There are several evidence-based interventions for distressed dementia caregivers that focus on skill building to increase resilience. However, few psychoeducational programs target Latino caregivers, and there are no evidence-based interventions promoting "social connectedness and support" in a culturally congruent way for Latinos. The Caregiver Thrive, Learn & Connect (TLC) is a telehealth caregiver educational program that builds upon evidence-based strategies from the "Coping with Caregiving" program (tested in REACH II) to improve caregivers' psychosocial outcomes. Caregiver TLC incorporates a goal-oriented approach focused on learning effective strategies to seeking support and connecting with caregivers and community resources. Dementia caregivers attend sessions in small groups through Zoom, making the program accessible for caregivers with limited information, time, transportation, and language proficiency. The program website allows caregivers to access information, resources (videos), attend informational activities (webinars) and participate in a virtual community where caregivers learn and connect with others.

Rationale: Several factors including distrust of the health system, language, and differences in cultural values contribute to the underrepresentation of Latinos in intervention research. There is urgency for culturally adapted programs addressing their needs. Our cultural adaptation follows the Barrera's Cultural Adaptation Behavioral Health Stage Model (2013).

Study Specific Aims: Specific Aim 1. To create a Community Advisory Board to engage Latino caregivers and community leaders to work with us to co-develop the program. Specific Aim 2. To test an early-stage adapted Spanish language of the program. Specific Aim 3. To examine the mechanism of social connectedness as a means to improve clinical outcomes (depression, stress, burden).

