*** 6. Data Analysis: Describe the analytical techniques the researcher will use to answer the study questions.**

Descriptive, bivariate and basic multivariate quantitative analyses (pre and post controlling by sociodemographic information). Data from focus groups will be analyzed using a content analysis approach.

*** 7. If there are procedures or methods that require specialized training, describe who (role and qualifications) will be involved and how they will be trained. e.g., cognitive assessments, specialized intervention or technique, blood draws, etc. If not, state not applicable.**

Facilitators will have a social work, case management or other human development or clinical background. Drs. [name] and [name] of the Optimal Aging Institute will train facilitators.

Identifiers

- * **1. Check the identifying information below that you have access to, already have, or will have, and or will receive, even if it is not retained with the research data. This includes any identifiers you may have at any point, even if only temporarily and even if the identifiers are never linked to the study data.**

- ☒ Names
- ☒ Telephone numbers
- ☒ All dates related to the subject (e.g. birth date, admission/discharge date, test date)
- ☐ Geographic subdivision smaller than a State (e.g. address, city, county, precinct, zip and geocode)
- ☐ Fax numbers
- ☒ Electronic mail addresses
- ☐ Social Security numbers
- ☐ Student or Employee ID numbers
- ☐ Device identifiers and serial numbers (e.g., implanted medical device)
- ☐ Certificate or license numbers
- ☐ Biometric identifiers, including finger and voice prints
- ☐ Account numbers (this could be any type of account that is unique to the participant)
- ☐ Health plan beneficiary numbers
- ☒ Full face photographic images and any comparable images
- ☐ Internet protocol (IP) address numbers
- ☐ Medical record numbers
- ☐ Vehicle identifiers and serial numbers (VIN), including license plate numbers
- ☐ Web universal resource locators (URLs)
- ☐ Any other unique identifying number, code or characteristic
- ☐ None of the above

Identifier Details

- * **2. For each of the items checked above, explain why this information will be collected and how it will be used.**

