materials; each initial meeting will focus on one workshop session and feedback will be obtained on: how content is presented; appropriateness of examples and action plans; how to increase social connectedness -particularly with family members – within the context of that workshop's focus. The CAB will also review the program Website that is in English, and make recommendations to make it user-friendly for Latino caregivers. The CAB will recommend ways to use this website to increase social connectedness. CAB members need to identify as Latino, be bilingual, and have the necessary time and skills to participate. To meet Aim 2 (Stage 1B trial), based on this feedback, a preliminary adapted version will be tested in an Stage 1B trial (pre- post design). We will recruit 20 Latino caregivers and all will receive the intervention (with n=10 in each group, run sequentially). We will make refinements (if needed) based on participant and CAB feedback between the first and second group. We will collect qualitative and quantitative data with several metrics (described below). Caregivers need to be men and women, 45 years and older, who identify as primary caregivers of a PLWD with whom they co-reside or live close by. A stress rating will be used so that at least a moderate level of stress related to caregiving is endorsed. Willingness to complete interviews and surveys and provide feedback are also necessary. To address Aim 3, (mechanisms) we will assess changes in loneliness and social support and anticipate that Latino caregivers who demonstrate decreases in loneliness and increases in social support will experience lower stress levels, burden and depression.

6. Analytic Plans: We will collect qualitative and descriptive quantitative data using mixed methods: 1. Individual semi-structured interviews with members of the CAB to ask them about caregivers' needs, supportive services, cultural views and normative expectations about care. 2. Data from Focus Group participants on feasibility and acceptability of the adaptation and refinement. 3. Descriptive pre-post data from the early developmental trial (20 caregivers). Data Analytics.

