What is/are the hypothesized principle(s) of the proposed intervention?	The intervention is proposed to work by helping caregivers create goals that are suitable to their life circumstances (per the Selection, Optimization, and Compensation model of lifespan development; Baltes & Baltes, 1990) and that address Latino cultural values. In particular, familism, a Latino cultural value underscoring prioritization of family above self, underlies a reliance on family members to provide dementia care, resulting in Latinos', among racial/ethnic groups, being among the lowest to access formal dementia care and support services. Familism can also contribute to caregiver depression, via behavioral disengagement (Parveen et al., 2013), or foster connectedness, when family support is strong. Familism is posited to be a necessary guiding principle in the development of interventions that can effectively target social connectedness (mechanism) to promote Latino caregiver well-being (health outcome). For example, psychoeducation to increase knowledge and priorities for social connectedness require attention to how familism may play a role in caregivers' resistance to rely on supports outside of the family.
How will the hypothesized mechanism(s) of behavior change be measured? How will the principles and mechanisms be tested?	The hypothesized mechanism underlying caregiver well-being is social connectedness. We will use social connectedness measures validated with Latino adults (PROMIS social isolation, PROMIS emotional support, Lubben Social Network Scale-6; UCLA-loneliness scale). To test the role of familism in intervention outcomes, we will examine (1) whether familism is associated with less social connectedness at baseline, and, (2) regardless of familism, whether the extent of change in social engagement (measured as uptake of social opportunities afforded by the intervention platform), explains social connectedness outcomes.

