- C) Measures of Social Connectedness, we will administer the following before & after intervention.

Lubben Social Network Scale-6, Spanish translation (culturally adapted as well as translated into Spanish; Vilar-Compte, Vargas-Bustamante & Lubben, 2018). It is a measure of social isolation (by identifying and counting people in the network including family/ friends and identifying who to talk with about private matters”.

UCLA Loneliness Scale by Vazquez Morejon, A.J., Jimenez Garcia-Boveda, R. 1994. RULS: Escala de Soledad UCLA Revisada. Fiabilidad y Validez de una version Española.

SPANISH: Items que componen la escala:

- 1.- Sintonizo (me llevo bien) con la gente que me rodea
- 2.- Me falta compañía
- 3.- No tengo a nadie con quien yo pueda contar
- 4.- Me siento solo/a
- 5.- Me siento parte de un grupo de amigos/as
- 6.- Tengo muchas cosas en común con la gente que me rodea
- 7.- No tengo confianza con nadie
- 8.- Mis intereses e ideas no son compartidos por las personas que me rodean
- 9.- Soy una persona abierta (extrovertida)
- 10.- Me siento cercano/a de algunas personas
- 11.- Me siento excluido/a, olvidado/a por los demás
- 12.- Mis relaciones sociales son superficiales
- 13.- Pienso que realmente nadie me conoce bien
- 14.- Me siento aislado/a de los demás
- 15.- Puedo encontrar compañía cuando lo necesito
- 16.- Hay personas que realmente me comprenden
- 17.- Me siento infeliz de estar tan aislado/a
- 18.- La gente está a mi alrededor pero no siento que esté conmigo
- 19.- Hay personas con las que puedo charlar y comunicarme
- 20.- Hay personas a las que puedo recurrir

Goal Setting and Attainment (SOC strategies)

D) Clinical outcomes: to be collected before & after early intervention trials:

Perceived Stress Scale, 10 item version (Cohen et al., 1983), available in Spanish

Zarit Caregiver Burden 6-item version (Higginson, et al., 2010), translated into Spanish (Martin-Carrasco et al., 2010)

PHQ-9 to assess depressive symptoms (Kroenke & Spitzer, 2002; available in Spanish).

E) Control factors such as:

Familism & Acculturation measures using the scales developed by Marin, Sabogal et al. (1987).

Appendix 4

EForm Name: Initial Application

Page: Study Attachments

Section: Attachments

Question: Upload Consent Materials

File Name: Program Consent Form Cuidando Juntos Consent form November 2023.docx

Appendix 5

EForm Name: Initial Application

Page: Study Attachments

Section: Attachments

Question: Upload Recruitment Materials

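### Aim 3 (social connectedness as mechanism) is not answered by the analysis as specified, and the documents disagree on whether a social support scale is administered

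*Combined protocol and SAP*

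**What the plan says.** Aim 3, stated in the IRB form and repeated in the grant application, is: "To examine the mechanism of social connectedness as a means to improve clinical outcomes (depression, stress, burden"). The grant's Research Design, item 5 (Study Design), turns this into an expectation: "we will assess changes in loneliness and social support and anticipate that Latino caregivers who demonstrate decreases in loneliness and increases in social support" will have lower stress, burden and depression.

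**Measures.** Three places list the connectedness scales.
- The grant's Background Questions name four: "PROMIS social isolation, PROMIS emotional support, Lubben Social Network Scale-6; UCLA-loneliness scale".
- Research Design item 6 (Analytic Plans, part b) names two, the Lubben Social Network Scale-6 (LSNS-6) and the 20-item UCLA Loneliness Scale.
- Appendix 3 (Project 9 Measures), item C, under "Measures of Social Connectedness, we will administer the following before & after intervention", names the same two and adds a goal-setting entry.

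Both of the last two lists describe the LSNS-6 in the same way: "It is a measure of social isolation (by identifying and counting people in the network including family/ friends", plus whom one can talk with about private matters. Perceived stress (PSS-10), burden (Zarit 6-item) and depression (PHQ-9) are collected before and after the program.

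**Analysis.** The Data Analysis Plan says that "the change in mean score from Time 1 to Time 2 for each outcome measure was evaluated", and then "Formal paired samples t-tests were conducted to test for statistical significance", with Cohen's d to help interpretation. The IRB form's item 6 (Data Analysis) says: "Descriptive, bivariate and basic multivariate quantitative analyses (pre and post controlling by sociodemographic information"). The Background Questions plan to relate familism to baseline connectedness, and change in social engagement to connectedness outcomes.

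**The concern.** Aim 3 asks whether the caregivers whose loneliness falls and support rises are the same caregivers whose stress, burden and depression fall. The quantity it needs is an association between individual changes. The one analysis set out in detail describes each variable's average change separately, so it gives no estimate of that association.

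As things stand, a fall in mean loneliness and a fall in mean depression could be reported side by side as support for the mechanism, even if the two changes are unrelated across caregivers. The pilot is meant to lead to a Stage II efficacy proposal, so that misreading would be carried into the rationale for the next trial.

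The support half of the expectation has a further problem. Neither list of scales to be administered names a support measure, so it is unclear what would stand for social support.

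**Working it through.** **Step 1. Match Aim 3 to each analysis statement.**

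| Place | What it relates | Gives change in connectedness against change in clinical outcome? |
|---|---|---|
| Data Analysis Plan | Each measure to itself, Time 1 to Time 2 | No |
| IRB form, item 6 Data Analysis | Unnamed variables, adjusted for sociodemographics | Not stated |
| Grant, Background Questions | Familism to baseline connectedness; engagement to connectedness | No, it stops at connectedness |
| Grant, Analytic Plans | Descriptive pre-post data | No |

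**Step 2. Match the measures.** PROMIS social isolation and PROMIS emotional support appear in the Background Questions and in neither of the other two lists. The goal-setting entry in Appendix 3 is not a support scale. The LSNS-6 touches on support through its private-matters element, but the documents present it as a measure of isolation. It is at best a partial proxy.

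**Step 3. Can separate t-tests carry information about the link?** A paired t-test depends only on the distribution of one variable's change, so its result does not depend on the correlation between two changes. A simulation shows this (n=20, 4,000 runs, standardised mean change of 0.7 in both variables; the 0.7 is assumed):

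| True correlation of changes | t-test 1 significant | t-test 2 significant | Correlation significant |
|---|---|---|---|
| 0 | 84.8% | 84.1% | 4.8% |
| 0.6 | 83.3% | 84.5% | 83.6% |

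The t-tests look the same in both rows. Only the change-on-change analysis separates them.

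**Step 4. What could a change-on-change analysis show?** The documents give no power calculation, effect size or alpha, so there is no figure to reproduce. The assumptions here are two-sided 0.05, 80% power, no dropout and independent participants. Sample size is 20 in the grant and 30 in the IRB form (cohorts of 10 and 20).

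Smallest detectable correlation by Fisher's z, with k covariates and 1.96 + 0.84 = 2.80:

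r = tanh(2.80 / √(n − 3 − k))

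- n=20, k=0: tanh(2.80/√17) = tanh(0.679) = 0.59
- n=20, k=2: tanh(2.80/√15) = tanh(0.723) = 0.62
- n=30, k=0: tanh(2.80/√27) = tanh(0.539) = 0.49

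The 95% interval for an observed r of 0.40 at n=20 is tanh(0.4236 ± 1.96/√17) = tanh(0.4236 ± 0.4754), or −0.05 to 0.72.

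Unadjusted power over a range of assumed true correlations:

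| True r | n=20 | n=30 | n for 80% power |
|---|---|---|---|
| 0.3 | 25% | 36% | 85 |
| 0.5 | 62% | 81% | 30 |

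**The case against.** The strongest reply is that the documents leave room for the missing analysis. The IRB form's data analysis item was written in answer to a question about techniques for the study questions, and bivariate and multivariate analyses could include a change-on-change model. That stands as far as it goes, but the item names no exposure, outcome or model, so it permits the analysis without specifying it.

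A reader might infer that Aim 3 cannot be answered at all. The documents do not support that. UCLA loneliness, LSNS-6, PSS-10, Zarit and PHQ-9 are all collected before and after, so the loneliness half can be explored without new data. Nor is support wholly unmeasured on paper. The Background Questions commit to PROMIS emotional support, and the IRB form says survey content is not yet fully developed. This is a conflict between lists.

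A reader might also infer a planned comparison of responders with non-responders from the grant's wording about caregivers who show decreases. No section defines such groups; the sentence states an expectation. A multiplicity penalty across scales and outcomes would likewise go too far. The IRB form states that there is no specific quantitative hypothesis, and related scales in the same people are not independent.

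On timing, the session outline (Appendix 2) polls progress on connecting goals in sessions 2 to 6, before the post-assessment. These polls are earlier data related to connectedness, but they are not loneliness or support scores, and no section links them to the clinical outcomes.

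Finally, this is an exploratory Stage I pilot that already acknowledges limited power. That lowers the severity. It does not remove the need to say which estimate answers a specific aim, particularly as the grant states a direction.

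**Conclusion.** The point holds in a limited form. No section specifies an analysis relating change in connectedness to change in stress, burden or depression, and the one detailed analysis cannot distinguish linked from unlinked changes. The measure lists contradict each other on social support. Both should be fixed, but neither prevents the pilot from running or makes Aim 3 unanswerable.

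Even with the right analysis the result will be imprecise. At n=20 only a correlation of about 0.59 (0.62 with two covariates) reaches 80% power, and an observed 0.40 would have an interval that includes zero. These figures rest on the assumed alpha, no dropout and independence between caregivers, although caregivers attend in groups; dropout would make them worse. They describe the precision of the added analysis and do not measure the size of the gap in the plan.

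With one arm, and with mechanism and outcome scales taken at the same two times, the most that Aim 3 can deliver is an association between changes. Mediation is out of reach.

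**What to change.** 1. **Reconcile the measure lists.** If the surveys are still open, include PROMIS Emotional Support at Time 1 and Time 2, and state whether PROMIS Social Isolation is kept. If data are already collected, as the past tense in the Data Analysis Plan may suggest, limit Aim 3 to loneliness and social network (LSNS-6) and remove social support from it.
2. **Add one exploratory analysis to the Data Analysis Plan.** For each of PSS-10, Zarit and PHQ-9, regress the Time 2 score on change in UCLA loneliness, kept continuous, adjusting for the Time 1 outcome and Time 1 UCLA. Report the slope with its 95% confidence interval. Name UCLA as the lead scale and the others as supportive. Put the emphasis on intervals rather than p-values, and say how this analysis relates to the sociodemographic adjustment promised in the IRB form.
3. **Reword the claim.** State that Aim 3 estimates the association between change in connectedness and change in clinical outcomes, and that the design does not allow a mediation claim.

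The cost is three simple regressions, possibly a few survey items at two time points, some wording, and a weaker statement for Aim 3. Concurrent measurement remains a limitation after these changes and should be reported as one.

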a. Metrics to assess acceptability of the adapted Caregiver TLC program at conclusion of the early stage trials studies: - Number of “hits” to website and program materials; - % completed action plans; - 6 point self-report Likert scales for: program satisfaction; new skills learned; usefulness of skills; helpfulness of skills; likelihood of using skills in future. b. To measure the mechanism of social connectedness, we will administer the following before & after intervention. - Lubben Social Network Scale-6, Spanish translation (culturally adapted as well as translated into Spanish; Vilar-Compte, Vargas-Bustamante & Lubben, 2018). It is a measure of social isolation (by identifying and counting people in the network including family/ friends and identifying who to talk with about private matters”); -To measure Loneliness we will use the UCLA Loneliness Scale (full version, 20 items). Feelings of loneliness maybe inversely related to feeling connected and supported by family and friends (Russell, Peplau & Cutrona, 1980). c) Clinical outcomes: to be collected before & after early intervention trials: - Perceived Stress Scale, 10 item version (Cohen et al., 1983), available in Spanish; - Zarit Caregiver Burden 6-item version (Higginson, et al, 2010), translated into Spanish (Martin-Carrasco et al., 2010), and PHQ-9 to assess depressive symptoms (Kroenke & Spitzer, 2002; available in Spanish). d) We also assess for the role of Familism and Acculturation using the scales developed by Marin, Sabogal et al. (1987). Highly acculturated Latino dementia caregivers are likely to more extensively use support services outside the home (and rely less on family) to care for PLWD.

7. Future Directions/ Next Steps: This work is regarded as preliminary to development of an Stage II efficacy trial grant proposal to submit in 2024 which will test the acceptability of the culturally adapted Caregiver TLC in a rigorous controlled trial. We aim to develop an RO1 level multi-site Stage III-IV trial to test the efficacy of this virtual adapted Caregiver TLC program with Latino caregivers in different parts of the US.

Background Questions:

Please answer the questions below in regard to your project. Not to exceed 1 page.

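### Neither analysis offered as a test of familism's role in intervention outcomes relates familism to a post-program outcome

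*Combined protocol and SAP*

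**What the plan says.** The main statement is in the grant application, Background Questions, in the answer on how principles and mechanisms will be tested. Analysis (1) is introduced as "To test the role of familism in intervention outcomes, we will examine (1) whether familism is associated with less social connectedness at baseline". Analysis (2) asks, "regardless of familism, whether the extent of change in social engagement", measured as uptake of the social opportunities on the platform, explains connectedness outcomes. The preceding answer treats familism as a necessary guiding principle of the intervention. It says familism can contribute to depression "or foster connectedness, when family support is strong".

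Familism appears in two other analysis-related places:

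- Grant application, section 6 (Analytic Plans), item d: "We also assess for the role of Familism and Acculturation using the scales developed by" a cited source. No model, outcome or contrast follows.
- Appendix 3 (Project 9 Measures), item 3 E: the familism scale is listed under "Control factors such as".

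Three other analysis statements do not mention it:

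- The Data Analysis Plan at the front of the document: "Formal paired samples t-tests were conducted to test for statistical significance", with Cohen's d alongside.
- IRB form, Data Analysis (item 6): descriptive, bivariate and basic multivariate pre-post analyses, adjusted for sociodemographic information.
- Grant application, section 5 (Study Design), Aim 3: changes in loneliness and social support are set against stress, burden and depression.

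**The concern.** A question about the role of familism in intervention outcomes needs at least one analysis in which familism is the predictor of interest and a post-program measurement is the outcome. Neither listed analysis has that form. A correlation at baseline describes the sample before anyone has attended a session. Caregivers high and low in familism could differ at baseline and have the same expected Time 2 score given where they started. They could equally start alike and end up differently.

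The practical stake is what is carried forward. The grant describes this pilot as preliminary to a Stage II proposal, and it uses familism to motivate the larger studies. If the baseline correlation is read under its present lead-in, it would be taken as evidence on a question it does not address, and the relevant estimate would not exist although the scales needed for it are already listed.

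**Working it through.** **Step 1. Match each analysis to the question.**

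| Analysis | Predictor of interest | Outcome | Post-program data? | Estimates familism's role? |
|---|---|---|---|---|
| (1) Background Questions | Familism | Baseline connectedness | No | No |
| (2) Background Questions | Change in engagement | Connectedness outcomes | Yes | No; familism at most a covariate |
| Data Analysis Plan | Time | Each outcome | Yes | No |
| IRB form, Data Analysis | Time, adjusted for sociodemographics | Not listed | Yes | Not named |
| Aim 3 | Change in loneliness and support | Stress, burden, depression | Yes | No |
| Analytic Plans, item d | Familism | None given | Not stated | No model given |
| Appendix 3, item 3 E | Familism as control factor | None given | Not stated | No model given |

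This mismatch needs no numerical assumption.

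**Step 2. Illustrate the consequence.** The plan gives no correlation, power or alpha for familism, so there is no figure to reproduce. Assumed: two-sided alpha 0.05; n=20 (grant) or n=30 (IRB form total); familism F standard normal; Time 1 score correlated rb with F; Time 2 = 0.7 × Time 1 + g × F + error, with g set to give partial correlation rc between F and Time 2 given Time 1. There were 8,000 replicates per setting. Analysis (1) is the Pearson test of F against Time 1. The comparison is the t-test of F in the regression of Time 2 on Time 1 and F.

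| n | rb | rc | Analysis (1) significant | Regression significant |
|---|---|---|---|---|
| 20 | -0.3 | 0 | 25% | 5% |
| 20 | -0.4 | 0 | 43% | 5% |
| 20 | -0.5 | 0 | 64% | 5% |
| 20 | 0 | 0.3 | 5% | 24% |
| 20 | 0 | 0.5 | 5% | 62% |
| 20 | 0 | 0.6 | 5% | 82% |
| 30 | -0.5 | 0 | 83% | 5% |
| 30 | 0 | 0.5 | 5% | 81% |

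Hand check of the first column of results by Fisher z, power = Φ(atanh(|r|)√(n−3) − 1.96), at n=20: for r=0.3, Φ(0.310 × 4.123 − 1.96) = Φ(−0.68) = 25%; for r=0.5, Φ(0.549 × 4.123 − 1.96) = Φ(0.31) = 62%, close to the simulated 64%.

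**Step 3. Analysis (2).** This was simulated at n=20 with change generated directly from familism and engagement. With no engagement effect it is significant in about 5% of trials whether or not familism affects change. With an engagement effect of 0.5 it is significant in 65% when familism has no effect on change and 64% when it has an effect of -0.5. With familism added as a covariate the figures are 62% and 77%. It reports on engagement throughout.

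**Step 4. Which null the regression tests.** The regression holds 5% when familism adds nothing to Time 2 given Time 1. That is not the same as raw change being unrelated to familism. With g=0, change = −0.3 × Time 1 + error. With error variance 0.51 (assumed), the correlation of familism with change is −0.3 × rb / √(0.09 + 0.51). For rb = −0.5 this is 0.15 / 0.775 = 0.19. Conversely, when raw change is made independent of familism, the regression rejects in about 8% to 11% of trials at n=20, and about 10% to 16% at n=30, as rb goes from −0.3 to −0.5. A plain correlation of familism with change stays at about 5%. The question therefore has to be worded to match the model.

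**Step 5. Precision at n=20.** The smallest correlation detectable with 80% power is tanh((1.960 + 0.842)/√17) = 0.59. An observed partial r of 0.5 has a 95% interval of tanh(0.549 ± 1.96/√16), or about 0.06 to 0.78.

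**The case against.** The best defense is that this is a short grant answer covering both principles and mechanisms: (1) speaks to the principle and (2) to the mechanism. The IRB form says there are no specific quantitative hypotheses, the grant calls the pre-post data descriptive, and the Data Analysis Plan concedes limited power. This stands and keeps the severity low. It does not make a baseline correlation informative about outcomes.

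Several stronger inferences are tempting, and the documents do not support them:

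- *That 25% to 64% is a false-positive rate.* It is the power of analysis (1) to detect a baseline correlation that the simulation built in. It misleads only if reported as an answer about outcomes. The lead-in invites that, but no passage commits the team to it.
- *That the plan leaves no room for covariates.* This is true of the paired t-tests, but the IRB form allows basic multivariate pre-post models. Those are described as adjusting for sociodemographics, and familism is not named.
- *That analysis (2) ignores familism.* Its wording can mean adjusted for familism, which fits the control-factor label in Appendix 3. A familism coefficient would then exist, but the plan does not name it as the test.
- *That analysis (1) is wrongly one-directional.* The positive direction is conditional on strong family support, and the grant says Latino caregivers report less of it. Expecting lower connectedness is consistent with that premise.

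**Conclusion.** The point holds as a mismatch between a stated question and the analyses listed for it. Neither analysis relates familism to a post-program outcome as the effect of interest, and no other section supplies one. This rests on the text alone.

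The size is illustrative. At n=20, analysis (1) is significant in about 64% of trials with a baseline r of −0.5 and no familism effect on Time 2 given Time 1, and in about 5% with a partial r of 0.5 and no baseline correlation. These figures depend on assumed associations; at a baseline r of −0.3 the 64% becomes 25%.

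A reader might also infer that the added regression would show whether familism modifies the program's effect. It would not. All participants receive the program, so the coefficient shows only whether familism predicts the Time 2 score given Time 1. It cannot separate program effect from change that would have happened anyway. Severity is low.

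**What to change.** In the grant application's Background Questions:

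1. Add one exploratory analysis for each connectedness outcome collected before and after the program: regress the Time 2 score on the Time 1 score and on familism measured at Time 1. Report the two-sided familism coefficient with its 95% CI. The Analytic Plans and Appendix 3 list the Lubben-6 and UCLA Loneliness scales for both occasions. The Background Questions also name two PROMIS scales; include them if they are collected at both.
2. State the question as whether baseline familism predicts Time 2 connectedness given Time 1 connectedness, and note that this differs from raw change when familism and baseline are correlated.
3. Keep (1) as a description of the sample at baseline and (2) as the engagement-mechanism analysis. Describe neither as a test of familism's role in intervention outcomes.
4. State that with one arm the coefficient is a prediction of pre-post outcome, not a modification of a treatment effect.
5. Say in Appendix 3 that familism is measured at Time 1.

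Alternatively, remove the reference to intervention outcomes from the lead-in and leave the two analyses as they are.

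The cost is wording plus one regression per outcome on scales already listed. The downside is a wide interval at n=20, with power of about 24% at a partial r of 0.3 and 62% at 0.5, so the result should be presented as an estimate and not as a confirmatory test.
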